- ^b. Patients will continue SC therapy to complete planned 108 weeks of total cemiplimab therapy (IV + SC combined), or until disease progression or unacceptable toxicity (For patients who initiate SC therapy after completing an even number of IV cycles, total planned duration of therapy would be 111 weeks). The maximum number of SC cycles would be 7 (Cycle 1-SC through 7-SC) for patients who begin SC therapy after completing 3 cycles of IV cemiplimab.
- ^c. For patients receiving Q3W SC cemiplimab, this should occur at least 60 days from day 1 of previous cycle, and no sooner than 18 days after the previous dose.
- ^d. Patient may sign consent for SC dosing at any time during the final IV cycle.
- ^e. The Day 8 visit in the first SC cycle is a PK-only visit for all patients who opt for SC cemiplimab. There is no Day 8 visit for subsequent SC cycles. See [Appendix 3](#).
- ^f. Complete physical examination includes head and neck, lungs, heart, abdomen, lymph nodes, extremities, and skin. A brief neurologic examination should also be performed. Exam should also include examination of site of SC injection to ensure local tolerability. The exam may be performed ≤72 hours prior to study treatment. Complete physical exam must be accompanied by assessment and documentation of ECOG Performance Status.
- ^g. Limited physical exam includes lungs, heart, abdomen, and skin.
- ^h. Vital signs include temperature, resting blood pressure, pulse, and respiration. Vital signs will be assessed and documented prior to the cemiplimab SC infusion, and then approximately 15 minutes after the completion of the cemiplimab SC injection(s). The allowable window for each specified time point is ±10 minutes.
- ^j. Hematology includes: WBC count, 3-cell differential (ANC, monocyte count, lymphocyte count), hemoglobin, and platelet count. Samples may be collected ≤72 hours prior to study treatment.
- ^k. Chemistry includes: sodium, potassium, chloride, bicarbonate, calcium, magnesium, phosphorous, glucose, albumin, creatinine, blood urea nitrogen (BUN), ALT, AST, total bilirubin, alkaline phosphatase (ALP), uric acid, and LDH. Samples may be collected ≤72 hours prior to study treatment.
- ^l. Pregnancy tests should be urine β-HCG, but serum β-HCG is also acceptable. Pregnancy tests are requirements for WOCBP only.
- ^m. Urinalysis: glucose, blood, pH, specific gravity, ketones, and spot urine protein.
- ⁿ. ADA samples will be collected at pre-dose on cycle 1 day1, cycle 3 day 1 and FU4 visit ([Table 9](#)).

█ [REDACTED]

█ [REDACTED]

█ [REDACTED]

█ [REDACTED]

█ [REDACTED]

█ [REDACTED]

^r. Adverse event recording will be ongoing throughout the course of the study.

^s. The EOS visit should occur 30 days (allowed window: 21 to 42 days) after the last dose of cemiplimab for patients who experience disease progression or withdraw consent. For patients who discontinue treatment for reason other than disease progression or withdrawal of consent, they should enter post-treatment follow up. See final footnote in Table 9 that specifies required duration of follow-up for patients who enter post-treatment follow up after SC dosing.

Table 9: Follow-Up (After Cycle 12 for Groups 1, 2, and 6 Patients; After Cycle 6 for Groups 3 through 5 Patients)

Study Procedure Visit	Follow-up 1	Follow-up 2	Follow-up 3	Follow-up 4 ^m	Follow-up 5	Follow-up 6	Follow-up 7 ^k	Extended Follow-up
Time point (Day)	Cycle 12 (Gps 1, 2, and 6) or Cycle 6 (Gps 3-5) visit + 28 ± 7 days	Follow-up 1 + 28 ± 7 days	Follow-up 2 + 28 ± 7 days	Follow-up 3 + 28 ± 7 days	Follow-up 4 + 28 ± 7 days	Follow-up 5 + 28 ± 7 days	Follow-up 6 + 28 ± 7 days	Every 4 months for 1 year ^l
Physical examination (complete) ^a	X	X	X	X	X	X	X	X
ECOG Status	X	X	X	X	X	X	X	X
Vital Signs ^b	X	X	X	X	X	X	X	X
Weight	X	X	X	X	X	X	X	X
Laboratory Tests								
Hematology ^{c, g}	X							
Blood Chemistry ^{d, g}	X							
Urine Pregnancy Test ^{e, g}	X							
Urinalysis ^{f, g}	X							
Serum IgG, IgM, IgE ^g	X							
Immune Safety Assays								
RF ^g	X							
ANA ^g	X							
TSH ^g	X							
CRP ^g	X							
PK Drug Conc/ADA Sample								
Cemiplimab PK/Drug Conc.	X	X	X	X			X	
ADA sample	X			X ⁿ			X	

Study Procedure Visit	Follow-up 1	Follow-up 2	Follow-up 3	Follow-up 4 ^m	Follow-up 5	Follow-up 6	Follow-up 7 ^k	Extended Follow-up
Time point (Day)	Cycle 12 (Gps 1, 2, and 6) or Cycle 6 (Gps 3-5) visit + 28 ± 7 days	Follow-up 1 + 28 ± 7 days	Follow-up 2 + 28 ± 7 days	Follow-up 3 + 28 ± 7 days	Follow-up 4 + 28 ± 7 days	Follow-up 5 + 28 ± 7 days	Follow-up 6 + 28 ± 7 days	Every 4 months for 1 year ^l
Pathology Samples								
Tumor biopsy ^e	←===== At Time of Progression =====>							
Tumor Assessments								
CT/MRI (chest/abdomen/pelvis) And/or digital photography ^h		X		X			X	X
Other Clinical Assessments								
Concomitant medications ⁱ	X							
Adverse events ^j	←===== >							

- ADA=anti-drug antibody; AE=adverse event; ANA=antinuclear antibody; CRP=C-reactive protein; CT=computed tomography; ECOG=Eastern Cooperative Oncology Group; MRI=magnetic resonance imaging; RF= rheumatoid factor; TSH=thyroid-stimulating hormone.
- a. Complete physical examination includes head and neck, lungs, heart, abdomen, lymph nodes, extremities, and skin. A brief neurologic examination should also be performed. Complete physical exam must be accompanied by assessment and documentation of ECOG Performance Status ([Appendix 7](#)).
 - b. Vital signs include temperature, resting blood pressure, pulse, and respiration.
 - c. Hematology includes: WBC count, 3-cell differential (ANC, monocyte count, lymphocyte count), hemoglobin, and platelet count.
 - d. Chemistry includes: sodium, potassium, chloride, bicarbonate, calcium, magnesium, phosphorous, glucose, albumin, creatinine, blood urea nitrogen (BUN), ALT, AST, total bilirubin, alkaline phosphatase (ALP), uric acid, and LDH.
 - e. Pregnancy tests may be urine β-HCG.
 - f. Urinalysis: glucose, blood, pH, specific gravity, ketones, and spot urine protein.
 - g. At time of progression, the EOS tumor biopsy should be obtained for all patients in Group 2 (see Section 6.2.2 and [Appendix 5](#)). Blood samples for laboratory tests (hematology, blood chemistry, urine pregnancy test, urinalysis, serum IgG, IgM, and IgE) and immune safety (RF, ANA, TSH, CRP) are also obtained at time of progression (within 28 days of the imaging study that documented progression) according to the EOS assessment schedule in [Table 3](#) and [Appendix 5](#). For Group 6 only TSH is required.
 - h. The same method (CT/MRI) and/or digital medical photography used at baseline should be used throughout the study. Scans linked to follow-up visits are required only if PD has not been confirmed previously while on study. CT/MRI imaging will be obtained within 14 days prior to the follow-up visit (per [Table 9](#)), so that the disease status is known at the time of the visit. Digital medical photography may be obtained within 14 days prior to visit, or on the day of the visit, and response status (CR, PR, SD, and PD) will guide whether the visit is to be treated as a follow-up visit or as the EOS visit.
 - i. Concomitant medications should be recorded from the date of informed consent through 30 days after last dose of study drug. Any drug started to treat a study drug-related AE during the follow-up will also be recorded. In addition, any cancer treatments should be recorded from the day of informed consent until 105 days (5 half-lives) after the administration of the last dose of cemiplimab. Any AE assessed as related to study treatment and persisting after 105 days (5 half-lives) post-last dose should be reported until resolution to baseline or grade ≤1.
 - j. Nonserious AE and SAE data will be collected from the day of informed consent until 105 days (5 half-lives) after the last dose of cemiplimab. Any AE assessed as related to study treatment and persisting after 105 days (5 half-lives) post-last dose should be reported until resolution to baseline or grade ≤1.

- k. After treatment and follow-up are completed or patients prematurely discontinue treatment and follow-up, patients will be followed quarterly for survival and tumor treatment status, if available. See Section 6.2.2.
- l. In Groups 1 to 5, patients who do not experience PD will be followed for an additional 1 year with assessments every 4 months. Patients in Group 6 will complete 6 months of follow-up (follow-up Visits 1 to 7 only) and will not go into extended follow-up after the 6-month follow-up is completed.
- m. For Group 6 patients who opt to switch to SC dosing and complete the Schedule of Events in Table 8, the only required follow up visits are Follow up visits 1-4. The last visit for these patients will be follow up 4, which provides sufficient long term safety follow up (> 105 days) after last dose of SC cemiplimab. These patients will not enter survival follow up.
- n. ADA collection at follow up visit 3 is only for Group 6 patients who switch to SC cemiplimab.

6.2. Study Follow-Up and Treatment Discontinuation

6.2.1. Unscheduled Visits

All attempts should be made to keep patients on the study schedule as specified in [Table 4](#) through [Table 9](#). Unscheduled visits may be necessary to repeat testing following abnormal laboratory results, for follow-up of AEs, or for any other reason, as warranted.

6.2.2. Follow-up

Patients who discontinue study treatment due to PD should return to the clinic 30 days (range: 21 to 42 days) after the last study treatment to complete the EOS assessments indicated in [Table 4](#) through [Table 9](#). After the EOS visit, patients should be followed for survival status until death, loss to follow-up, or study termination by the sponsor.

For all patients in Group 2, tumor biopsies ([Appendix 5](#)) should be obtained at time of progression, whether progression occurs in cycles 1 through 12 or during follow-up (after cycle 12).

Patients who discontinue study treatment due to reasons other than PD (eg, toxicity, confirmed CR after 48 weeks) should enter the follow-up schedule in [Table 9](#). (Note in clarification: Any patients who completed the posttreatment [Table 9](#) follow-up period of 6 months from previous amendments without disease progression will be asked to remain in follow-up. Such patients will be re-consented and asked to return approximately every 4 months (± 14 days) for 1 additional year to complete the extended follow-up assessments in [Table 9](#).)

For patients in Groups 1 or 2 who complete 12 cycles of treatment or for patients in Groups 3, 4, or 5 who complete 6 cycles of treatment without disease progression and subsequently experience disease progression during the follow-up period in [Table 9](#) without any intervening systemic anticancer therapy, resumption of treatment with cemiplimab 350 mg IV Q3W will be allowed. Prior to resumption of cemiplimab treatment, patients must be re-consented and repeat all screening activities (with the exception of providing new archived pathology material, or research biopsies), and the investigator must confirm that the patient still meets all eligibility criteria (other than the exclusion regarding prior treatment with anti-PD-1). Such patients will resume cemiplimab 350 mg IV Q3W for up to 108 weeks (maximum 12 retreatment cycles). The retreatment visit schedule will follow the study schedule in [Table 4](#). ADA samples will not be collected during retreatment. Patients in Group 5 who enter retreatment will not receive an additional dose of cemiplimab SC. For any patients who enter retreatment, the following are not required during retreatment: PK samples, research blood samples, and research tumor biopsies (exploratory tumor biopsies in Groups 2 and 4). *Note: Patients enrolled in Group 6 are not eligible for retreatment.*

After treatment, retreatment, and follow-up are completed or if patients prematurely discontinue from treatment, patients in Groups 1 to 5 will receive extended follow-up every 4 months for 1 year as per [Table 9](#). After this time, patients will be followed quarterly for survival and tumor treatment status, if available, until death. Survival follow-up status may be determined at clinic visits or via telephone contact with the patient, a family member of the patient, or the physician. Patients from Group 6 who discontinue cemiplimab early (before completing 108 weeks of treatment) for reasons other than disease progression will enter follow-up.

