5.3.3. Discontinuation of Study Treatment

Patients who permanently discontinue from study treatment and who do not withdraw from the study will be asked to complete the EOS assessments per [Table 3](#) through [Table 8](#), and then continue post-treatment follow-up visits per [Table 9](#) until disease recurrence to assure that data for the primary endpoint of the study is captured.

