- ^g. Vital signs include temperature, resting blood pressure, pulse, and respiration. Vital signs will be assessed and documented prior to the cemiplimab infusion, and then approximately 15 minutes after the completion of the cemiplimab infusion. The allowable window for each specified time point is ±10 minutes.

- h. Brain MRI with gadolinium is required at screening if not performed in the prior 60 days. Brain scans during the treatment and follow-up periods are required if there is a prior history of lesions present at screening or as clinically indicated. A brain CT with iodinated contrast may be performed if an MRI with gadolinium is contraindicated.
- i. Hematology includes: WBC count, 3-cell differential (ANC, monocyte count, lymphocyte count), hemoglobin, and platelet count. Samples may be collected ≤ 72 hours prior to study treatment.
- j. Chemistry includes: sodium, potassium, chloride, bicarbonate, calcium, magnesium, phosphorous, glucose, albumin, creatinine, blood urea nitrogen (BUN), ALT, AST, total bilirubin, alkaline phosphatase (ALP), uric acid, and LDH. Samples may be collected ≤ 72 hours prior to study treatment.
- k. Predose β -HCG (serum) at screening up to 72 hours prior to first administration. Subsequent pregnancy tests may be urine β -HCG. Serum pregnancy test and urine pregnancy test are requirements for women of child bearing potential only.
- l. Urinalysis: glucose, blood, pH, specific gravity, ketones, and spot urine protein. Samples may be collected ≤ 72 hours prior to study treatment.
- m. ADA samples are collected prior to treatment on day 1 of cycles 1, 3, and 5.
- n. Blood samples for PK will be collected at pre-infusion and end of infusion on days 1, 15, 29, and 43 of cycle 1, on day 1 of cycles 2 through 6, 7, 9, and 11. The final PK sample will be collected either at the EOS visit (for patients who discontinue treatment due to progression or toxicity during cycles 1 through 12) or at the follow-up visit 1 in [Table 9](#) (for patients who complete cycles 1 through 12). See [Appendix 3](#) for details on PK collection schedule.
- o. [REDACTED]
- p. [REDACTED]

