- q. The same method (CT with iodinated contrast or MRI with gadolinium) and/or digital medical photography used at baseline should be used throughout the study. For patients with locally advanced CSCC, guidelines for digital photography are provided in [Appendix 6](#). Imaging requirements differ for patients in Group 1 and Group 2; see Sections [6.3.1](#) and [6.3.2](#) for further details. On day 29, photos only for Group 2 patients need to be done. The intent of the photography is to show locations of the biopsies; formal response assessments are not planned for day 29 photos.
- r. Concomitant medication recording will be done at the start of each cycle, at a minimum. Concomitant medications should be recorded from the date of signing the ICF through follow-up visit 1 (posttreatment; [Table 9](#)).
- s. Adverse event recording will be ongoing throughout the course of the study, using NCI-CTCAE v4.03. See Section [7.2](#).
- t. (1) The EOS visit is for patients who experience PD requiring study discontinuation in cycles 1 through 12. This visit should occur 30 days (allowed window: 21 to 42 days) after the last dose of cemiplimab. The only posttreatment assessment that can occur outside of this timeframe is the posttreatment biopsy (required in Group 2) that can be obtained at any time within 28 days of last dose of cemiplimab. (2) Patients who complete the required events in [Table 3](#) (excluding the EOS visit) with any status other than PD (eg, CR, PR, or SD), or who discontinue treatment during cycles 1 through 12 for any reason other than PD, should go on to complete the assessments in [Table 9](#) (unless not possible, due to factors such as clinical decline or withdrawal of consent). These patients do not need to complete the EOS visit at end of cycle 12 as they will be assessed per [Table 9](#). After treatment and follow-up are completed or patients prematurely discontinue treatment and follow-up, patients will be followed quarterly for survival and tumor treatment status, if available.

Table 4: Study Schedule (Screening and Treatment) for Group 3

Study Procedure	Screening	Cycle 1				Cycles 2 – 6 ^a				End of Study
	-28 to -1	1	22±3	43±3	63±3	1 ^b	22±3	43±3	63±3	30 days after last dose of cemiplimab ^{s,t}
Clinical Assessments and Study Treatment										
Informed Consent ^c	X									
Genomics Substudy Informed Consent (optional)	X									
Medical/Oncology History	X									
Complete Physical Examination and ECOG PS ^d	X	X				X				X

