7.2. Recording and Reporting Adverse Events

7.2.1. Adverse Events

The investigator (or designee) will seek information on AEs at each patient contact and record all AEs that occur from the time the informed consent is signed until 105 days (5 half-lives) after the end of study treatment. After informed consent has been obtained but prior to initiation of study treatment, only the following categories of AEs should be reported on the AE electronic CRF:

- SAEs
- Nonserious AEs associated with a protocol-mandated intervention (eg, AEs related to an invasive procedure such as a biopsy)

(Other AEs that occur prior to first treatment should be reported on the medical history CRF.)

All AEs after initiation of study treatment and until 105 days (5 half-lives) after the last study treatment, regardless of relationship to study treatment, will be reported on the AE electronic CRF. Additionally, any SAE or other AE of concern that the investigator believes may be related to study treatment and that occurs later than 105 days (5 half-lives) after last study treatment should be reported.

Information on follow-up for AEs is provided in Section 7.2.6. Laboratory, vital signs, or ECG abnormalities are to be recorded as AEs as outlined in Section 7.2.5.

Group 5 patients and Group 6 patients who opt to receive SC dosing only: any local ISRs will be reported as AEs in the CRF, as appropriate.

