7.2.6. Follow-up

Information for any nonserious AE that starts during the treatment period or within 105 days (5 half-lives) after last treatment will be collected from the time of the event until resolution of the event, or until the patient's last study visit, whichever comes first.

Serious adverse event information will be collected until the event is considered resolved or chronic and/or stable.

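### Adverse events are to be collected to day 105 after the last dose, but patients who stop for progression have no scheduled safety contact after the end-of-study visit (day 21 to 42), and Table 9 gives other early stoppers no start point

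*Protocol*

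**What the plan says.** The two documents share the collection window. Protocol Section 7.2.1 tells the investigator to seek AEs at each patient contact and to "record all AEs that occur from the time the informed consent is signed until 105 days (5 half-lives) after the end of study treatment". Table 9 footnote j repeats the limit for serious and non-serious events. SAP Section 5.9 ends the on-treatment period 105 days after the last dose, or at the follow-up visit if that is later.

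*Stopping for PD.* Section 6.2.2 brings these patients back at day 30 (21 to 42) for EOS. It then says: "After the EOS visit, patients should be followed for survival status until death, loss to follow-up, or study termination by the sponsor". Table 9 footnote k makes survival follow-up quarterly. The last paragraph of Section 6.2.2 allows it in clinic or by telephone, with the patient, a relative or the physician. That paragraph also gives Groups 1 to 5 four-monthly extended follow-up for a year after premature discontinuation, without excluding PD. Table 9 footnote l limits extended follow-up to patients without PD.

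*Stopping early for other reasons.* Section 6.2.2 and Table 3 footnote t send these patients to Table 9, and the footnote states: "The EOS visit is for patients who experience PD requiring study discontinuation in cycles 1 through 12". Section 5.3.3 differs: "Patients who permanently discontinue from study treatment and who do not withdraw from the study will be asked to complete the EOS assessments per" Tables 3 to 8, before Table 9 visits until recurrence. Table 3 footnote n (PK) and Table 7 footnotes l and m (ADA and PK) place a sample at EOS "for patients who discontinue treatment due to progression or toxicity during cycles 1 through 12". Table 9 times Follow-up 1 at 28 ± 7 days after the "Cycle 12 (Gps 1, 2, and 6) or Cycle 6 (Gps 3-5) visit" and gives no other start.

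*Following an AE to its outcome.* Section 7.2.6 follows a non-serious AE to resolution or the patient's "last study visit, whichever comes first". Under Table 9 footnote j, a related AE that persists beyond 105 days "post-last dose should be reported until resolution to baseline or grade" 1 or lower.

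**The concern.** A collection window works only through the contacts inside it. Protocol Sections 5.3.2.1 and 7.2.3 both warn that immune-related AEs (irAEs) can appear several months after the last dose. If AEs are actively sought to about day 105 in patients who finish treatment without PD, but only to EOS in patients who progress, late events and their outcomes are ascertained less completely in the second set, and the difference follows disease outcome. SAP Section 5.9.1 counts both sets in the same safety denominator, so late event rates would tend to be understated by an amount nobody can recover afterwards.

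For patients who stop for toxicity the problem is different: it is unclear when their first post-treatment safety laboratory visit is due. Follow-up 1 is the only Table 9 column with routine hematology, chemistry and TSH. Nothing here touches the response rate, its confidence interval or alpha.

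**Working it through.** All days are counted from the last dose. The Table 9 cycle visit is taken as the end-of-cycle visit (an assumption).

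**1. The protocol's own check.** Table 9 footnote m says that Follow-up 4 falls more than 105 days after the last subcutaneous dose. With Table 8's 12-week cycles, the end-of-cycle visit is on day 85, and the last dose is on day 64 (Q3W) or day 43 (Q6W):
- Q3W: (85 − 64) + 4 × 28 = 133
- Q6W: (85 − 43) + 4 × 28 = 154

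The statement reproduces at nominal timing. With every window at its earliest, the Q3W figure is (21 − 6) + 4 × 21 = 99. No similar check is made for PD stoppers.

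**2. Patients who complete intravenous treatment.** Follow-up k = (end-of-cycle day − last dosing day) + 28k, with days from Tables 3 to 7.

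| Groups | Gap (days) | Follow-up 1 to 4 (day) | Visits by day 105 |
|---|---|---|---|
| 1, 2 | 56 − 43 = 13 | 41, 69, 97, 125 | 3 |
| 3, 5, 6 | 63 − 43 = 20 | 48, 76, 104, 132 | 3 |
| 4 | 56 − 29 = 27 | 55, 83, 111, 139 | 2 |

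**3. PD stoppers.** They have one visit, EOS. Days left without a scheduled safety contact:
- EOS at day 21: 105 − 21 = 84 (80%)
- EOS at day 30: 105 − 30 = 75 (71%)
- EOS at day 42: 105 − 42 = 63 (60%)

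**4. Contacts that might fill the gap.**
- Quarterly survival contact, taken as 91 days: day 91 if counted from the last dose; if counted from EOS, 21 + 91 = 112, 30 + 91 = 121 or 42 + 91 = 133. No start is stated, and the person reached need not be the patient.
- Four-monthly extended follow-up: 365.25 / 3 ≈ 122 days, so about day 122 at the earliest. It omits Group 6 and conflicts with footnote l.
- Section 5.3.3: its Table 9 visits run until recurrence, and a PD stopper has already progressed.
- Unscheduled visits (Section 6.2.1): these depend on someone already knowing of the event.

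None of these schedules a safety contact between EOS and day 105.

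**5. Other early stoppers.** The stated anchor does not exist for them. If the clock starts at the last dose, Follow-up 1 to 4 fall nominally on days 28, 56, 84 and 112, so Follow-up 4 passes day 105. With every interval at its shortest (21 days), Follow-up 4 is day 84 and Follow-up 5 is day 105.

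**6. Section 7.2.6 against footnote j.** Take a non-serious AE that starts on day 60 in a PD stopper. If EOS was the last study visit, the Section 7.2.6 end point passed before the event began. Footnote j gives an end point, but only for related events that persist beyond day 105.

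**The case against.** The duty to collect does not lapse at EOS. Section 7.2.1 requires all AEs to day 105 whatever their relationship to treatment, and a survival call that reaches the patient is a patient contact at which AEs must be sought. Section 7.2.2 requires serious AEs within 24 hours, and Section 6.2.1 allows unscheduled visits. SAP Section 5.9.1 counts an irAE at any time after the first dose as treatment-emergent, so a late irAE is analysed once it is reported. All of this stands. A reader might infer that PD patients have no safety contact after day 42; the documents do not say that. What is missing is a scheduled contact.

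A reader might also infer that patients who stop for toxicity are not followed to day 105, or that Follow-up 1 comes a year or more late. That needs a literal use of the Table 9 anchor that no site could apply. These patients are expressly sent to Table 9, and under Section 5.3.3 they would also have EOS laboratory tests. The defect is a missing start point and two conflicting routes.

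Two comparisons need care. A patient whose PD is found at the end-of-cycle assessment attends that visit too, so the fair contrast is 2 or 3 follow-up visits against one EOS visit. And the Table 20 row for leaving the study because of AE or PD does not count PD stoppers: it mixes the two reasons, concerns study rather than treatment discontinuation, and was compiled for progression-free survival.

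Finally, Groups 1 to 5 have completed enrollment, and Section 1.2.1 holds Amendment 9 until after the Group 6 primary data cut. A change made now would have limited reach.

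**Conclusion.** The point holds for scheduled contact. For PD stoppers the protocol places no safety contact between EOS and day 105, which leaves 60% to 80% of its own collection window to spontaneous reports, unscheduled visits or a survival contact that may not be with the patient. Whether that contact falls inside the window depends on an unstated start: about day 91 from the last dose, or day 112 to 133 from EOS, taking a quarter as 91 days. For other early stoppers follow-up is provided, but its start is undefined and Section 5.3.3 and the PK/ADA footnotes disagree with Section 6.2.2 and Table 3 footnote t.

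The number of patients affected and the number of late AEs missed cannot be derived from the documents. This is an inexpensive correction to safety ascertainment that should be made; it is no threat to the primary analysis.

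**What to change.** - **PD stoppers.** Time the first survival contact after EOS at about day 105 after the last dose, with the patient where possible, and complete the AE, serious AE and irAE-outcome pages at that contact.
- **Table 9.** For anyone stopping before the last planned cycle, anchor Follow-up 1 to the last dose of cemiplimab.
- **Routes.** Reconcile Section 5.3.3, both parts of Section 6.2.2, Table 9 footnote l and the footnotes of Tables 3 to 8, so that a single route (EOS or Table 9) applies to patients who stop for toxicity and the extended follow-up rule is the same throughout.
- **AE outcomes.** Reconcile Section 7.2.6 with Table 9 footnote j: related AEs followed as footnote j states, other non-serious AEs until resolution or the day-105 contact. Putting the footnote j rule in place of the Section 7.2.6 end point would not be enough, because unrelated non-serious AEs would then have no end point.

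The cost is protocol wording and the re-timing of a contact already planned, with no added visit. Reported late AE counts may rise slightly. The change reaches only patients still on treatment or within 105 days of their last dose.
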